4.10.3.2. Hypoglycemia Events

Both the rate per 1 patient year and incidence of the following type of hypoglycemia events will be derived and analyzed: documented hypoglycemia, documented nocturnal hypoglycemia (occurs between bedtime and waking), and documented non-nocturnal hypoglycemia (occurs between waking and bedtime).

[Table BDCM.1](#) provides the summary of statistical method for hypoglycemia event related analysis. Additionally, severe hypoglycemia events will be listed, and incidence of severe hypoglycemia will be compared between treatments using Fishers' exact test.

Table BDCM.1. Hypoglycemia Event Related Analyses

Endpoint	Time Point*	Statistical Method
Rate of hypoglycemia events defined by glucose <54 mg/dL (3.0 mmol/L) and ≤ 70 mg/dL (3.9 mmol/L) 
 • Documented • Nocturnal • Non-Nocturnal 	0-12, 0-32, 12-32 weeks, post-treatment period (up to Visit 801)*	Negative binomial regression with treatment, baseline SU use (yes/no), baseline HbA1c, baseline hypoglycemia event rate with the same category of the dependent variable, log (exposure in year) as the offset in the model.
Incidence of hypoglycemia events defined by glucose <54 mg/dL (3.0 mmol/L) and ≤ 70 mg/dL (3.9 mmol/L) 
 • Documented • Nocturnal • Non-Nocturnal 	0-12, 0-32, 12-32 weeks, post-treatment period (up to Visit 801)*	Logistic regression with treatment, baseline SU use (yes/no), baseline HbA1c, baseline hypoglycemia event rate with the same category of the dependent variable in the model. Note that the logistic regression will be conducted when ≥10 patients with this event.

 • Proportion of patients with HbA1c <7% without nocturnal hypoglycemia event • Proportion of patients with HbA1c ≤6.5% without nocturnal hypoglycemia event 	0-32 weeks	Logistic regression with treatment, baseline SU/meglitinide use (yes/no), baseline HbA1c, and baseline nocturnal hypoglycemia event rate in the model.

Abbreviations: HbA1c = hemoglobin A1c.

Note: The hypoglycemia rate per year during defined period is calculated by the number of hypoglycemia within the period/number of days patient at risk within the period*365.25 days. The hypoglycemia incidence during defined period indicates if the patient has at least 1 hypoglycemia events within the period (Yes/No). The baseline hypoglycemia rate is the rate calculated between Visit 1 and Visit 3.

*Analyses for endpoint during post-treatment period (up to Visit 801) will include all of the data after study drug discontinued on Safety population; analyses for endpoints during other time points will include all data before study drug discontinued on Safety population.

The following is the example of the SAS code of the negative binomial regression for analyzing the rate of hypoglycemia events.

```
proc glimmix empirical data=DATA;
class TREATMENT;
model HYPO_FREQ=TREATMENT [BASELINE_HYPO_RATE]
/dist=nb link=log offset=log(exposure in
days/365.25);
lsmeans TREATMENT/OM pdiff cl alpha=0.1 ilink;
random _residual_;
run;
```

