## 7.2. Method of Treatment Assignment

Study participants who meet all criteria for enrollment will be randomized to open-label treatment at Visit 3. Assignment to treatment groups will be determined by a computer-generated random sequence using an interactive web-response system (IWRS). The IWRS will be used to assign open-label IP to each study participant. Site personnel will confirm that they have located the correct IP by entering a confirmation number found on the IP label into the IWRS.

To achieve between-group comparability for site factor, the randomization will be stratified by country, baseline HbA1c (<8.5%, ≥8.5%), country, SU (yes/no), and baseline BMI (<30, ≥30). The randomization scheme will be performed using IWRS, which will ensure balance between treatment arms.

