4.7. Primary Outcome and Methodology

The primary efficacy measure of change in HbA1c at Week 32 (together with HbA1c measure at other postbaseline visits) will be summarized and analyzed using an MMRM approach on the EAS. This model implicitly adjusts for missing data through a variance-covariance structure. This model will include the fixed effects of treatment (LY3209590 Algorithm 1, LY3209590 Algorithm 2, insulin degludec), stratification factors (country, BMI strata [BMI <30 or ≥30], sulfonylureas use[Y/N]), visit, treatment by visit interaction, and baseline value of the dependent variable as the fixed effects. The HbA1c is reported in unit of % and will be converted to the unit of mmol/mol using the following formula: HbA1c in mmol/mol = 10.93*HbA1c in % - 23.5 (<http://www.ngsp.org/ifccngsp.asp>). HbA1c analysis will be conducted based on both units.

In the MMRM model, the within-patient errors are modeled as an unstructured variance-covariance matrix. If the analysis fails to converge, the following variance-covariance matrix will be used (in order) until one converges:

1. toeplitz with heterogeneity
2. autoregressive with heterogeneity
3. compound symmetry with heterogeneous variances
4. toeplitz
5. autoregressive
6. compound symmetry without heterogeneous variances

The Kenward-Roger approximation will be used to estimate denominator degrees of freedom for the MMRM models. The following is an example SAS code:

```
proc mixed data=DATA;
  class TREATMENT STRATIFICATIONS VISIT PATIENT;
  model HbA1c=BASELINE TREATMENT STRATIFICATIONS VISIT
        VISIT*TREATMENT / solution ddfm=kr;
  repeated VISIT / subject=PATIENT type=un;
  lsmeans TREATMENT*VISIT/ pdiff cl alpha=0.1 om=DATA;
run;
```

The 2-sided 90% CI for the LS mean for the individual treatment arms, treatment LS mean difference (LY3209590 Algorithm 1 vs. insulin degludec, LY3209590 Algorithm 2 vs insulin degludec, and LY3209590 Algorithm 1 vs LY3209590 Algorithm 2) in the change in HbA1c at 32 weeks will be constructed. Similar summary will be provided for the comparison between pooled LY arm and insulin degludec based on the contrast from the above MMRM model.

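### The hypoglycemia rate models in SAP Table BDCM.1 omit country and BMI stratum, two of the factors the trial randomises by, and may report a wider interval than the stratified design warrants

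*SAP*

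**What the plan says.** Protocol 7.2 sets the stratification: "the randomization will be stratified by country, baseline HbA1c (<8.5%, ≥8.5%), country, SU (yes/no), and baseline BMI (<30, ≥30" (country is listed twice). The SAP then treats these factors differently from one model to the next.

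- **HbA1c MMRM (SAP 4.7).** The fixed effects include "stratification factors (country, BMI strata" and sulfonylurea use. SAP 4.8 adds the HbA1c stratum for non-HbA1c efficacy measures, so those models carry all four factors.
- **HbA1c-target logistic model (SAP 4.8).** It includes country, BMI stratum, SU use and baseline HbA1c.
- **Hypoglycemia rate (SAP 4.10.3.2, Table BDCM.1).** "Negative binomial regression with treatment, baseline SU use (yes/no), baseline HbA1c, baseline hypoglycemia event rate", the last in the same event category as the outcome, with log exposure as offset.
- **Hypoglycemia incidence (same table).** "Logistic regression with treatment, baseline SU use (yes/no), baseline HbA1c, baseline hypoglycemia event rate with the same category" as the outcome, with the condition that the "logistic regression will be conducted when ≥10 patients with this event".
- **Example code for the rate model (SAP 4.10.3.2).** "model HYPO_FREQ=TREATMENT [BASELINE_HYPO_RATE" and a closing bracket, with no SU or baseline HbA1c term. It requests empirical (sandwich) standard errors.

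Hypoglycemia incidence and rate versus degludec are a secondary safety objective (SAP 3.2.2). Protocol 10.3.4.3 leaves the model to the SAP. BMI enters a hypoglycemia rate model only as a subgroup factor (SAP 4.12).

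**The concern.** When a trial is stratified on a factor that predicts the outcome, the arms are balanced on it and the treatment estimate is already largely free of its between-stratum variation. A model without the factor does not know this. It treats that variation as extra dispersion, and the standard error it reports tends to be too large. Here that would apply to the rate ratio for LY3209590 versus degludec, the main comparison of event rates in a trial of a weekly insulin.

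The SAP adjusts its efficacy models for country and BMI stratum and drops both from the rate models without comment. The covariate most likely to stand in for them is weak. The baseline event rate is taken between Visit 1 and Visit 3, about two weeks, and Protocol 9.2.2.1 has participants collecting episodes from Visit 2, about one week before randomisation. At an assumed 5 events per patient-year that is 5 × 7/365.25 = 0.10 to 5 × 14/365.25 = 0.19 expected events per person, so most values would be zero. It also predates CGM, which starts at Visit 3.

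**Working it through.** **1. The plan's own figure.** The only power figure is for HbA1c (Protocol 10.1): margin 0.4, SD 1.1, 200 pooled LY3209590 versus 100 degludec completers, two-sided alpha 0.10.

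SE = 1.1 × √(1/200 + 1/100) = 0.1347; 0.4/0.1347 − 1.645 = 1.324; power = Φ(1.324) = 90.7% (90.6% by noncentral t).

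The stated 90% reproduces, and this point does not affect it. No rate, dispersion or precision figure is given for hypoglycemia, so **every input below is an assumption**.

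**2. Rate model, sandwich standard errors.** Simulated 375 participants, 1:1:1, stratified blocks, 32 weeks, pooled LY3209590 versus degludec, 6 countries, 60% with BMI ≥30, dispersion 2, 600 runs per row. BMI log-rate effect is −0.2, or 0 where country SD is 0. Baseline event rate was not simulated. Each pair is without → with country and BMI stratum.

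| Control rate per year | Country SD (log rate) | True log rate ratio | Mean reported SE | Sampling SD | Rejection at 0.10 |
|---|---|---|---|---|---|
| 3 | 0 | −0.4 | 0.174 → 0.168 | 0.183 → 0.183 | 71.5% → 73.0% |
| 3 | 0.3 | −0.4 | 0.181 → 0.170 | 0.190 → 0.189 | 68.5% → 73.7% |
| 3 | 0.5 | −0.4 | 0.194 → 0.173 | 0.186 → 0.178 | 65.5% → 73.3% |
| 3 | 0.3 | 0 | 0.179 → 0.167 | 0.186 → 0.179 | 12.0% → 11.3% |
| 3 | 0.5 | 0 | 0.191 → 0.170 | 0.193 → 0.184 | 10.0% → 12.5% |
| 1 | 0.5 | −0.4 | 0.228 → 0.211 | 0.229 → 0.219 | 53.5% → 59.0% |

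The first row is the benchmark. With no prognostic effect the reported variance still falls by a factor of (0.174/0.168)² = 1.073, while the sampling SD does not move. That is the sandwich estimator shrinking as terms are added, not a gain. Removing it from the two matching rows:

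- country SD 0.3: (0.181/0.170)² = 1.134; 1.134/1.073 = 1.06
- country SD 0.5: (0.194/0.173)² = 1.258; 1.258/1.073 = 1.17

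Borrowing the same benchmark for the two null rows gives 1.07 and 1.18. The sampling SD is larger without the factors by 0.190/0.189 = 1.005 at the least and 0.193/0.184 = 1.049 at the most.

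**3. Rate model, other assumptions.** The first scenario has country SD 0.3 and BMI rate ratio 0.8; the second 0.5 and 0.7.

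| Setting | Reported variance ratio, without/with | Other results |
|---|---|---|
| 5 events/year, dispersion 1.2, 400 runs | 1.05; 1.14 | √1.14 = 1.07, a 7% wider 90% CI |
| Same scenarios, 6 countries, blocks of three within country-by-BMI cells, no treatment effect, 500 runs | 1.06; 1.17 | Sampling variance ratio 1.05; 1.10 (SD √1.05 = 1.025; √1.10 = 1.049) |
| 3 events/year, dispersion 1.5, two-week baseline count as covariate, model-based SE, 600 runs | 1.04; 1.09 | Power 78.0% v 78.8%; 74.2% v 76.7%. With no stratum effect the SE is unchanged (0.151) |

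**4. Incidence model.** In the first three scenarios of step 2, the SE of the log odds ratio rises on adjustment: 0.222 to 0.224, 0.225 and 0.228 (1% to 3%). The estimates move slightly away from zero (for example −0.303 to −0.320), and power changes by 0 to 2 points (39.3% to 39.3%, 34.5% to 35.2%, 40.3% to 42.3%).

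The planned logistic model has 6 parameters: intercept, two treatment terms, SU, HbA1c and baseline rate. With an assumed 6 countries, adding country and BMI makes 6 + 5 + 1 = 12, against a threshold of 10 patients with the event.

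**The case against.** No passage requires every model to carry every stratification factor. The SAP keeps its safety models small: laboratory measures, vital signs and weight, and ECG (SAP 4.10.4, 4.10.5, 4.10.7) carry no strata, and the protocol's logistic model for categorical AESIs has only treatment and HbA1c strata (Protocol 10.3.4.6). Hypoglycemia is adjusted more than these, with SU, continuous baseline HbA1c and the participant's own event history. The trial is Phase 2, hypoglycemia is not powered, and nothing in the documents shows that country or BMI is prognostic; listing BMI as a subgroup does not show it. Much of the apparent gain is conservatism in the unadjusted standard error rather than lost information.

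Most of this stands, and it limits the size of the point. It does not supply a reason for the omission. The lean safety models are a pattern, not a justification, and the two-week baseline rate can absorb only part of any country or BMI effect: with such a count in the model, the reported variance was still 4% to 9% larger without the strata.

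A reader might go further and infer that the incidence comparison also loses precision. Step 4 shows otherwise on the odds-ratio scale, and with fitting allowed from 10 patients with an event, leaving country out of that model is defensible.

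**Conclusion.** The point holds for the negative binomial rate models only, and it is modest and conditional. If country or BMI stratum predicts hypoglycemia beyond SU, baseline HbA1c and baseline event rate, the planned model reports a variance for the log rate ratio about 4% to 17% larger than a model with the two factors, net of the sandwich artefact. The true sampling SD is about 0% to 5% larger. If the factors do not matter, leaving them out loses nothing, and adding them costs nothing material.

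A reader might infer that the planned comparison is biased or invalid. The documents and the checks do not support that: stratified randomisation protects the estimate, and rejection under no effect was 10% to 12% without the factors in step 2. Nor can the loss be stated as fact, since every driving input is assumed. The power gains in step 2 should be read with caution, because the adjusted sandwich SE (0.170) sat below the sampling SD (0.184) in the strongest null case, where rejection was 12.5%.

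The mismatch between the example code and Table BDCM.1 needs no assumption. It stands on the text.

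**What to change.** - In Table BDCM.1, add country and BMI stratum (<30, ≥30) to the rate models, as in SAP 4.7. Pool small countries by a rule written down before database lock.
- Bring the example code in SAP 4.10.3.2 into line with the table: SU use, baseline HbA1c and baseline event rate, plus the two new terms.
- Leave the logistic incidence models as planned. If adjustment is wanted there, add BMI stratum and pooled region only as a sensitivity analysis where event counts allow, with the required count stated in advance.

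The cost is SAP wording and two model terms, with no change to data collection or sample size. The small downside is that sparse categories, such as nocturnal events below 54 mg/dL, may need coarser country pooling to converge. If the sponsor prefers the present model, a stated reason and a sensitivity analysis with the two factors would largely answer the point.

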## 9.2.2. Adverse Events of Special Interest

### 9.2.2.1. Hypoglycemia

Study participants will collect information on episodes of hypoglycemia starting from Visit 2 until the last study visit (Visit 801 or ET visit). For that purpose, study participants will be trained about signs and symptoms of hypoglycemia, how to treat hypoglycemia, and how to collect in study diary appropriate information for each episode of hypoglycemia according to the Schedule of Activities (Section 2). Site personnel will enter this information into the eCRF at visits indicated in the Schedule of Activities (Section 2).

Investigators should use the following definitions and criteria when diagnosing and categorizing an episode considered to be related to hypoglycemia (the PG values in this section refer to values determined by a laboratory or International Federation of Clinical Chemistry and Laboratory Medicine plasma-equivalent glucose meters and strips) (American Diabetes Association 2005):

- **Documented symptomatic hypoglycemia** is defined as any time a study participant feels that he/she is experiencing symptoms and/or signs associated with hypoglycemia, and has a PG level of  $\leq 70$  mg/dL ( $\leq 3.9$  mmol/L).
- **Asymptomatic hypoglycemia** is defined as any event not accompanied by typical symptoms of hypoglycemia but with a measured PG  $\leq 70$  mg/dL ( $\leq 3.9$  mmol/L).
- **Probable symptomatic hypoglycemia** is defined as an event during which symptoms of hypoglycemia are not accompanied by a PG determination (but that was presumably caused by a PG concentration  $\leq 70$  mg/dL [ $\leq 3.9$  mmol/L]).
- **Severe hypoglycemia** is defined as an episode requiring the assistance of another person to actively administer carbohydrate, glucagon, or other resuscitative actions. These episodes may be associated with sufficient neuroglycopenia to induce seizure or coma. Plasma glucose measurements may not be available during such an event, but neurological recovery attributable to the restoration of PG to normal is considered sufficient evidence that the event was induced by a low PG concentration.
- **Nocturnal hypoglycemia** is defined as any hypoglycemic event that occurs between bedtime and waking.
- **Total hypoglycemia** is defined as any event meeting the criteria for documented symptomatic hypoglycemia, asymptomatic hypoglycemia, or probable symptomatic hypoglycemia

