Baseline value for a variable is defined as the last nonmissing value for this variable prior to or at randomization visit (Visit 3), unless otherwise specified.

For continuous measurements, summary statistics will include sample size, mean, median, standard deviation (SD), minimum, and maximum. For certain variables that are considered to be log-normally distributed, the geometric mean and coefficient of variation (CV) will be provided instead.

For categorical measurements, summary statistics will include sample size, frequency, and percentages. Fisher's exact test will be used. Chi-squared test will be used for multi-category variables.

A mixed-model repeated measures (MMRM) model will be used for continuous outcomes with repeated postbaseline measurements to compare treatment arms, unless otherwise noted. Treatment comparisons will be performed for the treatment difference in least-squares means (LS mean). Means and LS mean by treatment group and visit, along with the standard error of LS mean, 90% CIs of the treatment differences along with the p-value for the treatment comparison will be displayed. For the change from baseline, p-value for the within-treatment comparison will also be displayed. For selected parameters, log-transformed values will be analyzed in the MMRM model instead. The actual, change from baseline and percentage change from baseline will be presented using the derivation based on the output from the MMRM model.

In this study, all negative binomial regression will estimate Group Mean instead of LS mean and use delta method to estimate the standard error of the Group Mean (Qu and Luo 2015). Group Mean is defined as the mean response in the treatment group for the studied population. The difference between LS mean and the Group Mean is that LS mean estimates the response by taking the inverse link function on mean covariates, while the Group Mean takes the inverse link function on individual patient covariates first and then averages over all patients.

All analyses will be implemented using SAS Enterprise Guide Version 7.1 or above.

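### The example code for hypoglycemia rates returns the LS mean that SAP 4.1 rejects and drops two required covariates, and the untransformed baseline rate can distort the Group Mean for frequent, highly dispersed events

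*SAP*

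**What the plan says.** **Model.** SAP Table BDCM.1 specifies a negative binomial regression for the rate, with treatment, baseline SU use, baseline HbA1c and "baseline hypoglycemia event rate with the same category of the dependent variable, log (exposure in year) as the offset in the model". Rates are annualised as the event count divided by "number of days patient at risk within the period*365.25 days". No transformation of the baseline rate is stated. SAP 4.12 uses the same terms for the subgroup analysis of rates.

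**Reported quantity.** SAP 4.1 says that "all negative binomial regression will estimate Group Mean instead of LS mean", with a delta-method standard error. It explains that "the Group Mean takes the inverse link function on individual patient covariates first and then averages over all patients", whereas the LS mean applies the inverse link at the mean covariates.

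**Example code.** The code in SAP 4.10.3.2 has the model line "model HYPO_FREQ=TREATMENT [BASELINE_HYPO_RATE", closed by a bracket, with a log link. It then requests "lsmeans TREATMENT/OM pdiff cl alpha=0.1 ilink". SU use and HbA1c do not appear, and no step computes a Group Mean.

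**Baseline window.** The SAP states: "The baseline hypoglycemia rate is the rate calculated between Visit 1 and Visit 3". Protocol 9.2.2.1 states: "Study participants will collect information on episodes of hypoglycemia starting from Visit 2 until the last study visit". The Schedule of Activities nevertheless marks hypoglycemia events at Visit 1.

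**The concern.** There are two separate problems.

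1. **The text and the code name different estimands.** A programmer who follows SAP 4.1 and one who follows the example code will report different rates per patient-year for the same arm. The code's covariates also differ from the table's.
2. **The baseline term may have the wrong shape.** The lead-in lasts about two weeks. On a log link, each further lead-in event multiplies the predicted on-treatment rate by the same factor. The Group Mean then averages the exponentiated predictions, so a few patients with several lead-in events can dominate an arm's rate.

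Incidence and rate of hypoglycemia are secondary safety endpoints, and Protocol 3.2 names hypoglycemia as the potential downside of a long-acting agent. Absolute rates may be carried forward, since the 12-week interim results are to inform later studies (Protocol 10.3.8, SAP 4.13).

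**Working it through.** The documents state no hypoglycemia rate, dispersion or power, so there is no figure of the plan's to reproduce here.

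**Step 1: the two estimators.** Write the linear predictor for patient i as η_i, for one year of exposure.

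- Group Mean (SAP 4.1): the average of exp(η_i).
- LS mean (example code): exp(average of η_i).

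By Jensen's inequality the coded value can never exceed the Group Mean from the same fit. The model has no treatment-by-covariate term and the average runs over all patients, so the covariate part cancels between arms. Both estimators therefore give the same rate ratio, exp(β).

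**Step 2: the shape of the baseline term.** One lead-in event is 365.25/14 = 26.1 per year, or 365.25/7 = 52.2 if collection starts at Visit 2. Five events in 14 days are 5 × 26.1 = 130 per year. Annualising is not itself the fault, since the coefficient rescales. The shape matters.

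Suppose patient rates are gamma distributed with mean μ and squared coefficient of variation k, and stay the same from lead-in to treatment. Given b events in a lead-in of t years, the expected rate is

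μ(1 + kb)/(1 + kμt),

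which is linear in b. At k = 2, successive events multiply the expected rate by 3/1 = 3, 5/3 = 1.67, 7/5 = 1.4 and 9/7 = 1.29. The log link with a raw rate forces one constant factor.

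**Step 3: simulation.** Taken from the protocol: 375 patients at 1:1:1, 20% dropout, 32 weeks of treatment and a lead-in of about 14 days. Assumed: event rates, dispersion k and lead-in/on-treatment correlation, with no treatment effect. SU use and HbA1c were left out, since no effect sizes are given.

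Median rates per year at correlation 1 (60 runs per setting), with the ratio to the true rate in brackets:

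| True rate, k | Group Mean, raw baseline | LS mean, as coded | Group Mean, log(baseline events + 0.5) |
|---|---|---|---|
| 3, k=2 | 2.96 (0.99) | 2.59 (0.86) | 2.87 (0.96) |
| 8, k=2 | 8.7 (1.09) | 6.6 (0.83) | 7.9 (0.99) |
| 12, k=2 | 15.3 (1.28) | 9.3 (0.78) | 12.1 (1.01) |
| 15, k=2 | 21.7 (1.45) | 11.6 (0.77) | 15.2 (1.01) |
| 8, k=4 | 17.3 (2.16) | 5.4 (0.68) | 8.5 (1.06) |

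The raw form is also unstable. At 8 per year and k = 3 its 5th to 95th percentiles were 8.0 to 110, against 6.1 to 10.2 for the log form.

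Further runs varied the correlation. Group Mean with raw baseline, divided by the true rate (ranges cover two sets of runs):

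| True rate, k | Correlation 1 | Correlation 0.7 | Correlation 0.5 |
|---|---|---|---|
| 8, k=2 | 1.12–1.16 | 1.03–1.04 | about 1.0 |
| 15, k=2 | 1.36–1.40 | 1.04–1.09 | about 1.0 |
| 8, k=4 | 2.2–2.49 | 1.18–1.27 | 1.0–1.09 |

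In one of these sets the coded LS mean was low by about 6 to 34%, and the Group Mean with a log-count covariate stayed at 0.95 to 1.03 of the truth.

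**Step 4: limits.**

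- *Low dispersion:* at k = 1 the raw Group Mean was 1.00 to 1.04 of the truth at every rate from 1 to 12 per year.
- *Not a small-sample effect:* with N = 30,000 and 6 per year, the ratio was 1.10 at k = 2 and 1.00 at k = 1.
- *Seven-day baseline:* medians were 0.94 to 1.94 with gamma rates and 0.97 to 1.11 with lognormal rates.
- *Other truths:* if the log rate really is linear in the raw baseline rate, or the baseline is unrelated, the raw Group Mean was 0.98 to 1.02. In the first case a log(count + 1) term fell to 0.79 in the most extreme setting (12 per year, k = 4).
- *Rate ratio:* simulated medians were 0.94 to 1.04 for a true ratio of 1.

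**The case against.** **The code is only an example.** Its offset is written in words, and its bracketed covariate resembles the stratification placeholder in the code of SAP 4.7. SAP 4.1 names the estimator and Table BDCM.1 names the covariates, so the analysis is prespecified. This lowers the severity. It does not remove the conflict: the `lsmeans` line is concrete, it asks for the quantity that 4.1 sets aside, and nothing in the code leads to a Group Mean.

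**The inflation needs a strong link between lead-in and treatment.** The design weakens that link. Participants switch insulin at randomization and are titrated, real-time CGM with alarms starts only at Visit 3, and Protocol 7.8.2.2 has therapy reduced after repeated or severe events. This objection stands. A reader might infer that the model always inflates the arm rates; the documents give no rate, dispersion or correlation to support that.

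**The comparison between arms is safe.** This also stands. A reader might infer a biased treatment effect, but the rate ratio is the same under either estimator. No decision rule in the documents uses a modelled absolute rate.

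**Gross inflation would be noticed.** It would be in part, because a crude annualised rate is derived for each patient. The SAP does not, however, require it beside the modelled rate.

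**Conclusion.** The conflict between SAP 4.1, Table BDCM.1 and the example code is certain from the text and should be resolved before programming. If the code is followed, per-arm rates are too low, by about 6 to 34% under the assumed rates and dispersion.

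The effect of the raw baseline rate is conditional. For frequent, highly dispersed categories with strongly correlated lead-in and treatment rates, the Group Mean is inflated by about 0 to 40% at dispersion 2 (45% in the most extreme setting run), and more than doubled at 8 per year with dispersion 4. For rare, mildly dispersed or weakly correlated events it is about nil. Some of the <54 mg/dL and nocturnal rows may well fall there.

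Only absolute rates, and differences formed from them, are at stake. A reader might also infer that the logistic incidence models need the same change. That is not supported: the Group Mean rule covers negative binomial regression only, and no logistic result was computed.

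**What to change.** 1. **Replace the example code in SAP 4.10.3.2.** Include treatment, SU use, baseline HbA1c and the baseline hypoglycemia term. For each arm, set treatment to that arm for every patient and exposure to one year, exponentiate each prediction, average over all patients, and attach the delta-method standard error. Do not report the `lsmeans` `ilink` value as the rate.
2. **Change the baseline term in the negative binomial rate models (Table BDCM.1 and 4.12).** For example, use log((baseline events + 0.5)/lead-in days at risk), with the raw rate as a sensitivity analysis. Keeping days at risk matters because the visit windows (±7 and ±3 days) make the lead-in length vary. Leave the logistic incidence models as they are.
3. **Print crude events per patient-year beside each modelled rate.**
4. **Reconcile the baseline window.** Settle Visit 1 or Visit 2 as its start, consistently with Protocol 9.2.2.1 and the Schedule of Activities, and count events and days at risk over the same interval.

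The cost is SAP wording and code, with no new data. The drawback is that the added constant is arbitrary. Under the gamma model the matching constant is 1/k, so 0.5 fits k = 2 by construction. The log form can also understate the rate if the log rate is truly linear in the raw baseline rate, which is why the raw form is kept as a sensitivity analysis.
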